 - i. Go into QlikView and find transfer call record
 - ii. Update:
 1. Patient Class of the Related Admission
 2. Payor
 3. Transfer type
 4. Transfer outcome
 5. Destination facility

6. Cancel reason (if applicable)
 - a. If cancel reason in QlikView doesn't match what is in the note, record what is in QlikView and then make a comment under the RP comments section.
2. Mark the form as complete if all fields are filled out for the record (i.e., final study status for each provider [can not be pending] and the associated fields with the transfer)

[figure not shown]
Supplemental Files

Supplemental File 1: EGS conditions

Common medical terms and abbreviations (if not found below): <https://www.health.harvard.edu/a-through-c#A-terms>

General terms

- Things seen on imaging
 - Pneumoperitoneum – air outside of the intestine but inside the abdomen
 - Pneumatosis – air in the wall of the intestine – may or may not require surgery; can be seen if the intestine is dilated or if there is ischemia (dead)
- Tubes
 - NG tube – nasogastric tube – tube that goes into the nose → esophagus → stomach; used for drainage when there is a perforation or blockage
 - Dobhoff tube – tube that goes into the nose → esophagus → stomach →; used for feeding
 - G-tube – gastrostomy tube – tube that goes through the abdominal wall into the stomach – can be used for drainage or feeding

©ADAM A PEG is a type of G-tube

-
- J-tube – jejunostomy tube – tube that goes through the abdominal wall into the intestines (jejunum) – used for feeding
- G-J tube – a G-tube that has an extension that goes into the small intestine
- Hematoma – collection of blood
 - Rectus sheath hematoma – bleeding into the muscles of the abdominal wall
- Stricture – narrowing
- Fistula – connection between two things that shouldn't be connected
 - Arteriovenous fistula – connection between artery and vein
 - Colovesicular – connection between the colon and the bladder
- Terms related to timing of diseases
 - Acute (new issue)
 - Chronic (old issue)
 - Acute on chronic (flare up of a long-term problem)
- Omentum – layer of fat in the abdomen
- Tumors
 - Can be benign or malignant (cancer)
 - If malignant, can start in organs in the abdomen or start somewhere else and then go to organs in the abdomen

Miscellaneous diagnoses

- Sepsis/Septic shock/Systemic Inflammatory Response Syndrome (SIRS) – various terms to indicate that an infection is making a person sick beyond the infection itself
- Obstruction (blockage) – often referred to the intestine but could be other organs as well

[figure not shown]
- Abscess – collection of infection; can be anywhere – skin or soft tissue (fat), solid organ (liver, spleen, pancreas), intra-abdominal (in the abdomen – typically after a surgical procedure or due to a perforation of the intestine)
 - Usually requires either drainage through an incision or by Interventional Radiology putting in a drain
- Peritonitis – the peritoneum is the lining of the inside of the abdomen – so when there is something wrong in the abdomen patients develop irritation of the peritoneum, called peritonitis

Hepatobiliary diseases (Liver-bile duct diseases)

- Gallbladder
 - Cholecystitis – infection of the gallbladder; can be acute or chronic; can be due to gallstones or acalculous (without gallstones)
 - Cholelithiasis – stones in the gallbladder without infection
 - Biliary colic – symptomatic gallstones
- Liver
 - Usually related to infection (abscesses) or tumors (e.g., hemangiomas)
- Bile duct – connects the liver to the small intestine
 - Choledocholithiasis – stone in the bile duct
 - Cholangitis – infection in the bile duct usually because there is a stone blocking the bile duct
 - Cholangiocarcinoma – bile duct cancer

Hemorrhage (bleeding)

- Hemoperitoneum
 - Bleeding into the abdomen or retroperitoneum [back of the abdomen] but not into the lumen of the intestines
 - Can be due to solid organs (liver [hemangioma], spleen, pancreas) bleeding due to non-traumatic causes (usually tumors)
- Gastrointestinal (GI) bleed
 - Bleeding into the lumen of the intestines
 - Usually from a gastric or duodenal ulcer or from the colon (diverticulosis [outpouchings of the colon])
 - Rarer causes are arteriovenous (AV) malformations (where the artery-vein make an abnormal connection); one example is a Dieulafoy lesion

Necrotizing soft tissue infections

- Necrotizing fasciitis
- Gangrene
- Fournier's gangrene
- Before the infection gets this severe, it often starts as cellulitis

[figure not shown]
Hernia

- Inguinal
- Femoral
- Umbilical

- Ventral
- Incisional
- Parastomal (Intestines around an ostomy)
 - Pancreas is behind the stomach
 - Small intestines: duodenum, jejunum, ileum
- Diaphragmatic (stomach into the chest)

Motility disorders of the intestines (not due to a blockage)

- Ogilvie syndrome
 - Acute dilation of the colon seen in critically ill patients
 - Treatment: treat primary cause of illness; may need colonoscopy or rectal tube for decompression; may need surgery if it gets so big that the intestine dies or perforates
- Ileus
 - Common after surgery or when the patient has another disease process going on
 - Intestines don't work or contract (peristalsis) but there is no blockage
 - May require NGT; often improves on its own with fixing the primary problem

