Care coordination for older patients with emergency general surgery (EGS) diagnoses suffers because conversations between referring and accepting providers regarding decisions to transfer between acute care hospitals are ineffective, incomplete, and inefficient. To standardize a method to support transfer decisions that is tailored to older adults within extant transfer processes, we will (Aim 1) engage key stakeholders to develop an intervention to Support Interhospital Transfer Decisions (SITe) for older EGS patients by adapting an existing intervention for interhospital handoffs. Then, through Aim 2, we will assess the acceptability of the SITe intervention, test the feasibility of study procedures, and explore efficacy outcomes for evaluation in a future, larger clinical trial. Using a pre-post design, we plan to study 100 transfer calls of older EGS patients to our tertiary care center over an anticipated six-month period. We will collect data from chart reviews, transfer center logs, and Qualtrics surveys. We define adequate acceptability as >85% utilization of the tool. We define fidelity to the tool as <15% missing patient information. We will measure the rate of survey completion for study-eligible transfer calls and examine rates of and reasons for missing data on our outcomes. To prepare to test intervention effectiveness in a future study, we will measure the potential to avoid transfer, efficiency of communication, emotional labor, and patient health outcomes.

Pre-Existing Information/Background Knowledge

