Modeling a similar, successful pilot, we will conduct a pre (control)/post (intervention) study with an anticipated 50 transfer calls in each arm. We will collect pre- and post-intervention data after each eligible transfer call through (1) chart review and access center logs and (2) Qualtrics surveys of referring providers and UW (accepting) providers. We will collect baseline (pre) and post-intervention measures of the potential to avoid transfers, efficiency of transfer communication and execution, provider emotional labor, and patient health outcomes. Providers will utilize the SITe intervention during transfer calls discussing transfer decisions regarding older emergency general surgery (EGS) patients. The research team will be listening retrospectively to recordings of eligible transfer calls through the Calabrio System to observe whether key elements of the intervention items were discussed during the calls. The Calabrio System is a recording system that automatically records transfer calls for the UW Health-Meriter Access Center. Supervisors and managers can access the Calabrio Call Recording Management portal by going to: <https://calabrio.uwhealth.wisc.edu>. We will request access to the Calabrio system and listen to eligible transfer calls directly in the system and will not download any recordings.

Participants:

- Patients: We will include all calls from referring providers requesting transfer of emergency general surgery patients age 60 and older from a referring ED or inpatient floor to the UW ED or inpatient floor.
- Providers: We will include all UW (accepting) surgeons and all referring providers who execute transfer calls of eligible patients. There will be no exclusions regarding referring providers’ position (e.g., physician, mid-level provider), specialty (e.g., emergency medicine, internal medicine), or affiliation (e.g., UW or non-UW).

SITe Intervention Training:

- UW (accepting) surgeons: We will complete SITe intervention training over two months. Utilizing the implementation toolkit developed by stakeholders in Aim 1, we will hold web-based seminars at various dates and times to accommodate differing schedules.

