- Referring providers: Consistent with our focus on information “receivers” and because it is not feasible to train all potential referring providers, at the start of the intervention training, the PI will send a letter and email to referring providers who have transferred EGS patients to UW. We will introduce the SITe intervention as part UW’s goal of optimizing communication regarding transfer decisions. We will describe our intervention and procedures for data collection, and provide contact information. UW Physician Liaisons will also promote the study.

Data collection:

We anticipate collecting data on approximately 50 patient transfer calls in each pre- and post-intervention period. Based on recent data, we expect each period to last approximately five months. Research staff will screen AC logs and reference

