We will not conduct formal tests of efficacy given concerns about inadequate power and sampling error in a pilot of this size. However, we will compare pre-post outcomes to understand the measures and to inform the design of a future, larger clinical trial.

Data Protection:

All communication with providers will be via a secure UW email account. For providers who prefer texting, we will only text links and reminders and not text any personal information. Information collected in this study will be kept on a secure computer within the Department of Surgery network, which is protected by a firewall that ensures the privacy of the network. The data will be stored in a restricted access folder on the department server. Access to the information is limited to those listed in the protocol, all of whom have completed the requisite human subjects/HIPAA training. While the team may incidentally hear non-eligible call recordings as we search for eligible calls, we have created processes to minimize the extent to which we are exposed to protected health information outside of the study purview. We will also attend a virtual training of 30 minutes or less at the UW-Meriter Access Center to orient our team to the Calabrio call system.

Risks and Benefits

This is a pilot study; therefore, we have no evidence-based information about the potential benefits to subjects. Stakeholders who develop the transfer decision intervention may benefit from knowing that they are helping to design an intervention that may benefit future Access Center nurses (ACNs), providers, and patients. While it is not known if participants will benefit from the pilot study, providers may experience a benefit from receiving intervention trainings to improve communication surrounding decisions to transfer older emergency general surgery patients. Patients and their surrogates may benefit from any improvements in communication. The risks of this pilot study are outweighed by the benefits, as the study poses minimal risk to participants and those who participate may benefit by knowing that they are helping future ACNs, providers, and patients.

Potential Benefits to Society

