This pilot study engages key parties involved in or impacted by decisions regarding interhospital transfers. Our transfer decision intervention could better address the needs of transferred older adults with emergency general surgery diagnoses and standardize the communication regarding decisions to transfer. In the future, this transfer decision intervention could potentially contribute to improving the health outcomes of approximately 240,000 older patients transferred for surgical emergencies in the United States.

Subject Population

Total Subjects: 212

Inclusion Criteria

Human subjects in Aim 2 of this study include:

Patients: We will include all calls from referring providers requesting transfer of emergency general surgery patients age 60 and older from a referring ED or inpatient floor to the UW ED or inpatient floor. We will do an initial chart review to identify eligible transfer calls.

Providers: UW (accepting) surgeons and referring providers who execute transfer calls of eligible patients. There will be no exclusions regarding referring providers' position (e.g., physician, mid-level provider), specialty (e.g., emergency medicine, internal medicine), or affiliation (e.g., UW or non-UW).

Subjects include 12 UW (accepting) surgeons, 100 patient transfer calls, and 100 referring providers. These numbers assume that each patient is unique and a unique referring provider calls to transfer.

Exclusion Criteria

Providers who do not speak English, prisoners, patients younger than 60 years old, and interhospital transfers other than for EGS diagnoses will be excluded.

Recruitment Plan

Patients:

We will not directly recruit patients but request a waiver of consent as the study involves chart review and could not be practically carried out without a waiver.

All providers (pre- and post-intervention survey completion):

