To encourage participation, at the beginning of the study, the PI will send a letter and email to UW (accepting) surgeons and referring providers who have transferred EGS patients to UW. We will do Google searches and explore referring facility pages to obtain contact information for CMOs and referring providers. We will also utilize a service called RocketReach [<https://rocketreach.co/>] to obtain contact information of CMOs and providers. RocketReach is a legally compliant tool that allows users to find emails and phone numbers of individuals. Its search technology scans for publicly available contact information on third party websites such as social media sites, corporate websites, and public records. Our team will create an account and pay a monthly fee for this service. Obtaining contact information is key to distributing study information and contacting referring providers for eligible transfer calls. Additionally, leadership from Wisconsin Surgical Society and Wisconsin Chapter - American College of Emergency Physicians will also be asked to help us spread the word about this study. Additionally, we will also collaborate with the UW Health Physician Liaison team and our current EGS stakeholder group to help us distribute information about this study to referring providers and request provider's preferred contact information. Leadership, the Physician Liaison team, and EGS stakeholder group will utilize scripts and flyers to only share information to create awareness of study and will not be enrolling or interacting further with eligible participants. Informational materials and scripts describe our procedures for administering the Qualtrics survey, what participation entails, provide contact information for questions, feedback, or concerns, but will not introduce the intervention until the post-intervention period. After each eligible transfer call, our study team members will invite the involved providers to participate in the study by emailing with a link to complete the survey. We will also send texts to providers who prefer to receive the survey links and reminders via text. We will send reminder emails and/or text to providers who have not completed the survey before their deadline. We will obtain electronic consent for each survey. We will not be providing incentives to referring and accepting providers as advised by the UW Health legal department and leadership. Incentivizing providers after every eligible transfer call may be perceived as incentivizing referring providers to transfer to UW Health or accepting providers to take more transfer calls, which violates anti-kickback statutes.

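### Does the summary's six-month forecast for 100 transfer calls conflict with two five-month periods in a way that requires a change?

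*Protocol*

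**What the plan says.** The opening summary, describing a pre-post design, states: "we plan to study 100 transfer calls of older EGS patients to our tertiary care center over an anticipated six-month period". The sentence covers both periods together and names a single six-month span.

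Under Study Procedures and Interventions, the design is given as "we will conduct a pre (control)/post (intervention) study with an anticipated 50 transfer calls in each arm". The Data collection text repeats the count, "We anticipate collecting data on approximately 50 patient transfer calls in each pre- and post-intervention period", and adds a length: "Based on recent data, we expect each period to last approximately five months". Training of the accepting surgeons is a separate item: "We will complete SITe intervention training over two months". The protocol does not say where those two months fall relative to the two periods.

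The Subject Population section again has 100 calls: "Subjects include 12 UW (accepting) surgeons, 100 patient transfer calls, and 100 referring providers".

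On inference, the Data analysis text says: "We will not conduct formal tests of efficacy given concerns about inadequate power and sampling error in a pilot of this size".

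**The concern.** Two current statements in one protocol forecast different durations for the same 100 calls: six months in the summary, and twice five months in the Data collection text. In a before-after study at one receiving centre, the control period has to end before the intervention period begins, so the two lengths add up and cannot overlap.

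The study is also a pilot. Testing feasibility is one of its aims, and it is meant to inform a larger trial. The accrual rate is among the first figures a planner would take from such a study. A reader of the summary alone would infer a rate about two-thirds higher than the Data collection text supports, or would expect collection to end about four months too early. If collection were in fact closed after six months, fewer calls than planned would be available.

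**Working it through.** **Inputs**

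- Summary: 100 calls, 6 months, both periods together.
- Data collection: about 50 calls per period, about 5 months per period.
- Study Procedures and Interventions: pre (control) then post (intervention), 50 calls each; training over 2 months, place in the calendar not stated.
- Subject Population: 100 calls in total.

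**Rate and duration from the Data collection text**

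- Rate = 50 / 5 = 10 calls a month.
- Time for 100 calls = 100 / 10 = 10 months, which is 2 × 5.
- Difference from the summary = 10 − 6 = 4 months.
- If the training falls between the two periods (an assumption), the calendar is 10 + 2 = 12 months.

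**Rate implied by the summary**

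- 100 / 6 = 16.7 calls a month, which is 16.7 / 10 = 1.67 times the other rate.
- At that rate, 50 calls take 50 / 16.7 = 3.0 months, not five.

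**Can another reading make six months work?**

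| Reading | Result |
|---|---|
| Six months covers both periods, at 10 calls a month | 6 × 10 = 60 calls |
| Six months also includes the two months of training | 4 × 10 = 40 calls |
| Six months is meant for each period | 50 / 6 = 8.3 calls a month; six against five months per period |
| The periods overlap | Ruled out by the pre/post design |

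None gives 100 calls in six months at the Data collection rate. Chance does not bridge the gap either: if calls arrive as a Poisson process at 10 a month (an assumption), the expected number in six months is 60, and the probability of 100 or more is about 1.5 in a million. The third reading almost closes the gap, but it strains the summary's wording, which attaches one six-month span to all 100 calls.

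The 60 and 40 in the table only test the readings. They do not forecast a shortfall, because nothing in the protocol closes collection at six months.

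**Does anything use the duration?**

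- *Sample size:* fixed by call count, and consistent in all four places (100 in the summary and in Subject Population; 50 per period in the design statement and in Data collection).
- *Acceptability and fidelity thresholds:* use of the tool above 85% and missing patient information below 15%. Both are proportions, with no time in the denominator.
- *Power:* no calculation is given, and formal efficacy tests are expressly excluded.
- *Stopping:* no rule refers to elapsed months.
- *Pre-post comparison:* descriptive, on the calls collected in each period.

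The duration therefore enters no calculation or decision that the protocol describes.

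**The case for a change.** The strongest case for acting is that this is a genuine contradiction between two complete, current sentences. It is not an omission that a statistical analysis plan would fill, and an analysis plan would not normally correct the protocol's own summary. Words such as anticipated and approximately allow for modest drift, but not for six months against ten. A pilot that reports on feasibility should state its expected accrual coherently, and the repair is only a change of wording.

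Most of that stands. The arithmetic is right and the two statements should agree. What does not follow is any consequence for the trial. Staff would work from the Data collection text, which is the operative passage and the only one that gives a basis for its figure. They would collect about 50 calls per period whatever the summary says. A later trial would presumably be planned on the accrual this pilot observes, not on a forecast in its summary.

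Two supporting points are also weaker than they look. The protocol does not show which duration is out of date. The reference to recent data favours five months per period, but the summary could be the intended figure, in which case the Data collection text would be the one to correct. And the statement in the Recruitment Plan, "will not introduce the intervention until the post-intervention period", concerns informational materials and scripts, not the intervention schedule. That the periods run in sequence rests on the pre/post design itself, which is enough.

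**Conclusion.** The inconsistency is real but clerical. At the Data collection rate of about 10 calls a month, 100 calls need about 10 months of collection, training not counted, against the six months in the summary: a gap of four months in a planning forecast. If six months was loosely meant for each period, the gap is about one month per period.

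No change to the plan is needed. Collection is defined by call count, the count is consistent throughout, and no threshold, stopping rule, power figure or analysis depends on the months. No recruitment shortfall is implied. The two sentences can be brought into line at the next routine edit, whichever figure the sponsor intends.

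This conclusion assumes that collection continues until the call targets are met, which is how the protocol frames its size. It would need another look if a fixed six-month cut-off applied, but the protocol states none.

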the electronic medical record to identify eligible patients, UW (accepting) surgeons, and referring providers. We will collect data via review of UW electronic health records and AC logs. Within approximately 48 hours of each qualified transfer, we will email the UW (accepting) provider and referring provider who executed the transfer an approximately three-minute, personalized Qualtrics survey, to be completed at their convenience within an anticipated three days. A survey will be sent during the pre- and post-intervention period. We will also text providers who prefer texting to receive survey links and reminders. We will send reminder emails and/or text to providers who have not responded the surveys before their due date. Since this study is considered a clinical trial, for reporting and grant purposes, we will track provider and patient demographics such as age, gender, and race. We will send accepting providers a pre-survey form requesting their contact information, texting preferences, and request consent to listen to their transfer calls. RPs will be asked to provide demographic information and consent for listening to recordings when taking the actual SITe survey. We have included recording consent language in the surveys. We will listen to eligible transfer call recordings during the pre and post intervention phases to observe if intervention items were discussed during the call. We will listen to call recordings only if both the AP and the RP provide consent to the recording portion of this study. If both providers do not consent to the recording portion, we will review the Access Center notes. No protected health information or patient or provider details will be recorded. The call recordings will stay in the Calabrio system and not be downloaded.

Data analysis:

We will apply descriptive statistics for counts and ordinal measures. We will summarize free text responses regarding AP's perspectives on the following statements:

- "I felt that the reason for transfer was justifiable"
- "I felt that the referring hospital should have been able to care for the patient."
- "I felt respected by the referring provider."

We will also summarize free text responses regarding RP's perspectives on the following statements:

- "I felt that the UW Surgeon doubted whether the transfer was necessary."
- "I felt respected by the UW Surgeon."

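### Does the pre-post comparison of health outcomes need changing because patients who never reach UW have no named source of hospital course?

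*Protocol*

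**What the plan says.** Eligibility is set by the request, not by its result. Under Participants, and again under Inclusion Criteria, the protocol states: "We will include all calls from referring providers requesting transfer of emergency general surgery patients age 60 and older". Inclusion Criteria adds "We will do an initial chart review to identify eligible transfer calls". The Exclusion Criteria do not remove requests that are denied or cancelled.

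Non-arrivals are expected. The Standard Operating Procedure (Section 4) has staff update the transfer outcome, "Destination facility" and, where relevant, the reason for cancellation. The invitation email in Supplemental File 2 has options for accepted, denied and pending requests.

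For patient data, the Data collection section says: "We will collect data via review of UW electronic health records and AC logs". The surveys ask providers about the call and do not supply a hospital course.

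On the tool: "Providers will utilize the SITe intervention during transfer calls discussing transfer decisions regarding older emergency general surgery (EGS) patients". On outcomes, the opening summary says "we will measure the potential to avoid transfer, efficiency of communication, emotional labor, and patient health outcomes". It also undertakes to examine how often, and why, outcome data are missing. The Data analysis section rules out formal efficacy tests because of limited power and sampling error, and then says "we will compare pre-post outcomes to understand the measures and to inform the design of a future, larger clinical trial".

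**The concern.** The eligible unit is the call, but the hospital course is visible only through UW records. Whether a patient has an observed outcome therefore depends largely on whether the transfer goes ahead. That is the decision the tool is meant to inform, and the scope for avoiding transfer is itself one of the explored measures.

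If the tool led to fewer transfers of patients who could be managed locally, the post-period arrivals would be a sicker group. Their average outcomes would look worse although no patient had fared worse. If instead it kept sicker patients from being moved, the arrivals would look better. Either way the comparison is conditional on something that happens after the intervention. A larger sample would not remove the selection, so the stake is a misleading planning input for the future trial more than a false result in this pilot.

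**Working it through.** **The plan's own figures.** Subject Population gives 12 accepting surgeons + 100 patient calls + 100 referring providers = 212, which reproduces the stated total. The 100 calls are 50 + 50. Neither figure rests on a power calculation or on a count of arrivals, so no stated number is in dispute.

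**Is the dependence real?** Setting the sections side by side:
- Participants and Inclusion Criteria: all requesting calls are eligible.
- Standard Operating Procedure (Section 4) and Supplemental File 2: some requests end in denial or cancellation.
- Data collection: UW records and Access Center logs are the record sources. The log fields that staff update later are administrative (patient class, payor, transfer type, outcome, destination, cancel reason).

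It follows that hospital-course outcomes are in practice confined to patients who reach UW, apart from any non-arrivals who happen to have a UW record.

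**How large could a shift be?** Take the Background section's figures for transferred patients as the pre-period values among arrivals: length of stay 4.3 days (treated as a mean), mortality 4.4%, morbidity 38.8%. Let *a* be the share of arrivals averted in the post period and *m* the mean or rate those patients would have had. With no patient's own outcome changed,

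arrivals after = (value before − *a* × *m*) / (1 − *a*).

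Assume *a* = 0.10 to 0.27. The upper end is the Background's ceiling for potentially avoidable transfers; it is not a forecast. If all 50 calls would otherwise lead to arrival, this removes 50 × 0.10 = 5 to 50 × 0.27 = 13.5 calls. All values of *m* below are assumptions, except that 26.1% is the Background's morbidity rate for directly admitted patients, here assumed to apply to averted ones.

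| Outcome | *a* | *m* | Arrivals after | Shift |
|---|---|---|---|---|
| Stay | 0.10 | 1 day | (4.3 − 0.10)/0.90 = 4.67 | +0.37 days |
| Stay | 0.10 | 3 days | (4.3 − 0.30)/0.90 = 4.44 | +0.14 days |
| Stay | 0.27 | 1 day | (4.3 − 0.27)/0.73 = 5.52 | +1.22 days |
| Stay | 0.27 | 3 days | (4.3 − 0.81)/0.73 = 4.78 | +0.48 days |
| Mortality | 0.10 | 0% | 4.4/0.90 = 4.89% | +0.49 points |
| Mortality | 0.10 | 10% | (4.4 − 1.0)/0.90 = 3.78% | −0.62 points |
| Mortality | 0.27 | 0% | 4.4/0.73 = 6.03% | +1.63 points |
| Mortality | 0.27 | 10% | (4.4 − 2.7)/0.73 = 2.33% | −2.07 points |
| Morbidity | 0.27 | 26.1% | (38.8 − 7.05)/0.73 = 43.5% | +4.7 points |
| Morbidity | 0.27 | 38.8% | (38.8 − 10.48)/0.73 = 38.8% | 0 |

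**Against sampling error.** For a difference in proportions with 50 arrivals before and 50(1 − *a*) after, SE = √[p₀(1 − p₀)/50 + p₁(1 − p₁)/(50(1 − *a*))].
- Mortality, *a* = 0.27, *m* = 0: √[0.044 × 0.956/50 + 0.0603 × 0.9397/36.5] = 4.89 points, against a shift of 1.63.
- Mortality, *a* = 0.27, *m* = 10%: √[0.044 × 0.956/50 + 0.0233 × 0.9767/36.5] = 3.83 points, against 2.07.
- Morbidity, *a* = 0.27, *m* = 26.1%: √[0.388 × 0.612/50 + 0.435 × 0.565/36.5] = 10.7 points, against 4.7.

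No standard deviation for length of stay is given, so the same comparison cannot be made there.

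**What the table cannot show.** The sign for mortality follows the assumed *m*, and the shift is zero when averted patients resemble the rest. The loss of 5 to 13.5 calls supposes that every pre-period request ended in arrival. The email with the denied option is the pre-intervention version, so non-arrivals are expected in that period too; fewer calls would then be lost at the same *a*. The protocol does not forecast a fall in transfers.

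**The case for a change.** The strongest case for a change runs as follows. Every link is documented, and the protocol's own model has the tool acting on the decision that governs observation. An unseen SAP could define an analysis set, but it could not supply outcomes from a source the protocol does not name. The Data analysis section gives the comparison a purpose, the design of a larger trial, and sampling error shrinks with sample size whereas this selection does not. The remedy is cheap: tabulate call outcome by period from fields already recorded, and label the health outcomes as arrivals-only.

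The structural part of this stands, including that no source is named for patients treated elsewhere. The step to a required change does not, for three reasons.
- The protocol does not itemise the health outcomes or say they will be analysed for all calls, so no stated analysis is contradicted. The analysis set and the layout of tables are ordinary SAP content.
- The planned look at missing outcome data, with the recorded transfer outcome, destination and cancel reason, already shows how many calls lack a UW course and why. The proposed table and label describe the selection just as those do; they neither remove it nor add a source of data.
- Nothing in the protocol says an unadjusted difference will be carried forward as the tool's effect, or that the larger trial will count arrivals only. A rule against doing so would forbid something not proposed.

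**Conclusion.** The observation is right but calls for no change. Comparisons of patient health outcomes will in practice be restricted to patients who reach UW, and they could shift if the share or mix transferred differs between periods. Size and direction cannot be derived from the document. The illustrative shifts (0.1 to 1.2 days; up to about 2 points of mortality in either direction; 0 to about 5 points of morbidity at the 27% ceiling) rest on assumed averted shares and assumed outcomes in averted patients. The mortality and morbidity shifts lie within the pilot's sampling error.

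This is a gap that analysts fill sensibly in a descriptive 100-call pilot. A careful report would say that the outcomes cover arrivals, and would give the proportion transferred and the number of calls without a UW outcome in each period. The fields and the missing-data review needed for that are already in the protocol. The conclusion assumes that the missing-data review is carried out as stated, and that the health-outcome differences are read as exploratory, as the Data analysis section intends.
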